#### **12.6.5.5.2 Physical Examination**

Physical examination data recorded at the Screening, Day -1, Day 5 or at early termination will be listed (Listing 15.3.6.7). Subject's data with abnormal and abnormal clinically significant physical examination findings will be flagged.

The number and percentage of subjects with normal, abnormal and abnormal clinically significant results will be tabulated by body systems at each recording time point (Table 15.2.6.15).

#### **12.6.5.5.3 Vital Signs**

Vital signs (systolic and diastolic blood pressure, pulse rate and respiratory rate) will be measured at Screening, Day -1 and on every day of confinement (from Day 1 to Day 5/early termination). From Day 1 to Day 4, vital signs will be assessed within 60 minutes prior to product use and 60 minutes  $\pm$  10 minutes after each product use period (fixed puffing regimen and *ad libitum* use). Every measurement of vital signs has to be assessed as normal or abnormal and, if abnormal, as clinically significant or not clinically significant. A diagnosis has to be provided in the CRF for all measurement of vital signs assessed as abnormal and clinically significant.

#### **Confidentiality Statement**

Vital signs values, changes from baseline (i.e. Day -1 or pre-fixed puffing measurement) and normality evaluation will be listed (Listing 15.3.6.8).

Descriptive statistics will be presented for values and changes from baseline and the number and percentage of subjects with normal/abnormal not clinically significant/abnormal clinically significant results will be reported by P3P variant and time point (Tables 15.2.6.16.1, 15.2.6.16.2, 15.2.6.16.3 and 15.2.6.16.4).

#### **12.6.5.4 Spirometry**

Spirometry parameters (FEV1, FEV1 % predicted, FVC, FVC % predicted, FEV1/FVC) will be measured at Screening and Day 5 or early termination. Every measurement of spirometry parameters has to be assessed as normal or abnormal and, if abnormal, as clinically significant or not clinically significant. A diagnosis has to be provided in the CRF for all measurement of spirometry parameters assessed as abnormal and clinically significant.

Spirometry predicted values will be standardized to the National Health and Nutrition Examination Survey III predicted set (Hu and Cassano, 2000).

Spirometry parameters, changes from baseline (i.e. screening) and normality evaluation will be listed (Listing 15.3.6.9).

Descriptive statistics will be presented for values and changes from baseline and the number and percentage of subjects with normal/abnormal not clinically significant/abnormal clinically significant results will be reported by time point (Tables 15.2.6.17.1 and 15.2.6.17.2).

#### **12.6.5.5 ECG**

The ECG measurements will be obtained directly from the 12-lead ECG traces, i.e. not centrally read. These measurements (heart rate, PR interval, QRS duration, QT interval, QTcB interval, QTcF interval) will be measured at Screening, Day -1 and on every day of confinement (from Day 1 to Day 5/early termination). On Day 1 to Day 4, ECG will be assessed post fixed puffing regimen and post *ad libitum* use. Every measurement of ECG has to be assessed as normal or abnormal and, if abnormal, as clinically significant or not clinically significant. A diagnosis has to be provided in the CRF for all measurement of ECG assessed as abnormal and clinically significant.

ECG measurements, changes from baseline (i.e. Day -1) and normality evaluation will be listed (Listing 15.3.6.10).

Descriptive statistics will be presented for measurements and changes from baseline and the number and percentage of subjects with normal/abnormal not clinically significant/abnormal clinically significant results will be reported by P3P variant and time point (Tables 15.2.6.18.1, 15.2.6.18.2).

### **12.6.5.5.6 Assessment of Cough**

Cough questionnaire is assessed on Day -1 prior to product test and prior to product use on Day 2, 3, 4 and 5. Questionnaire details are reported in Section 7.3.5 "Cough Assessment".

The answer to the Cough questionnaire will be listed (Listing 15.3.6.11).

The number and % of subjects reporting a cough will be summarized at baseline and after product use. The responses to the individual items, including the VAS evaluating the level of cough bother and 3 Likert scales measuring the intensity, the frequency of cough and the amount of sputum production will be listed and summarized at baseline and change from baseline by P3P variant, for all subjects who filled in the questionnaire. The answers to the open question related to any other important observation will be listed only (Table 15.2.6.19).

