7.8.5 Cough Assessment

Subjects will be asked if they have experienced a regular need to cough, e.g., whether they have coughed several times in the previous 24 hours prior to assessment. If the answer is 'yes', they will be asked to complete a cough assessment questionnaire (which includes a VAS, three Likert scales, and an open question).

The VAS will assess how bothersome cough is to the subject ranging from 'not bothering me at all' to 'extremely bothersome'.

Furthermore, subjects will be asked to assess the intensity and frequency of cough and the amount of sputum production on Likert scales:

- The intensity of cough will be assessed on a 5-point Likert scale ranging from 1 to 5:
1 = very mild; 2 = mild; 3 = moderate; 4 = severe; 5 = very severe.
- The frequency of cough will be assessed on a 5-point Likert scale ranging from 1 to 5:
1 = rarely; 2 = sometimes; 3 = fairly often; 4 = often; 5 = almost always.
- The amount of sputum production will be assessed on a 4-point Likert scale ranging from 0 to 3:
0 = no sputum; 1 = a moderate amount of sputum; 2 = a larger amount of sputum; 3 = a very large amount of sputum.

Cough assessment will be conducted at Admission prior to product test and 24 hours (± 1 hour) after product use (T_0 fix) for each variant (Day 2 through Day 5). Cough assessment should be done in the morning prior to any product use.

Confidentiality Statement

Data and information contained in this document are considered to constitute trade secrets and confidential commercial information, and the legal protections provided to such trade secrets and confidential information are hereby claimed under the provisions of applicable law. No part of this document may be publicly disclosed without the written consent of Philip Morris Products S.A.

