12.1.4 Handling of Missing Values and of Values outside the Detection Limits

In general, missing data will not be imputed in this study, due to the nature of the measurements and the short periods of exposure and use. However, for questionnaire data total scores and domain or subscale scores may use a certain degree of imputation by averaging across individual item scores. Further details will be provided in the SAP.

In general, values below the lower limit of quantification (LLOQ) will be imputed using $0.5 \times$ lower limit of quantification. For values above the upper limit of quantification (ULOQ), i.e.,

Confidentiality Statement

Data and information contained in this document are considered to constitute trade secrets and confidential commercial information, and the legal protections provided to such trade secrets and confidential information are hereby claimed under the provisions of applicable law. No part of this document may be publicly disclosed without the written consent of Philip Morris Products S.A.

preceded by a “>”, for example “>xx,” the numerical xx will be used for calculation and reporting in summary tables.

The number and percent of values below LLOQ or above ULOQ will be presented in each summary table.

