#### Confidentiality Statement

- Per-puff parameters and per-product use experience parameters

4. To estimate the amount of powder aerosolized from P3P from the fixed puffing regimen and the *ad libitum* use periods.

Endpoint:

- Weight difference of P3P before and after use

5. To monitor the safety and tolerability during the study.

Endpoints:

- Incidence of adverse events (AEs), serious adverse events (SAEs)
- Frequency of AEs, SAEs
- Incidence of P3P product events including malfunction/misuse
- Frequency of P3P product events including malfunction/misuse
- Physical examination changes from baseline
- Cough changes from baseline (VAS and three Likert scales)
- Electrocardiogram (ECG) changes from baseline (heart rate, PR, QRS, QT, QTcB, QTcF intervals)
- Vital signs changes from baseline (systolic and diastolic blood pressure, pulse rate and respiratory rate)
- Spirometry changes from baseline (FEV1, FEV1 % predicted, FVC, FVC % predicted FEV1/FVC)
- Changes from baseline in clinical chemistry, hematology, and urine analysis safety panel
- Concomitant medications

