### 7.3.5 Cough Assessment

Subjects will be asked if they have experienced a regular need to cough (e.g., coughing several times) in the last 24 hours prior to assessment. If the answer is 'yes', they will be asked to complete a visual analogue scale (VAS), three Likert scale questions and an open question assessing their cough during previous 24 hours.

The VAS will assess how bothersome cough is to the subject ranging from 'not bothering me at all' to 'extremely bothersome', and this will be given a numeric value between 0 and 100.

Subjects will also be asked to assess the intensity and frequency of cough and the amount of sputum production on Likert scales as presented in Table 10.

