**Table 10 Cough Assessment Likert Scales**

Question	Likert Scale
1 How intense is your cough?	1 = very mild 2 = mild 3 = moderate 4 = severe 5 = very severe
2 How frequently do you normally have to cough each day?	1 = rarely 2 = sometimes 3 = fairly often 4 = often 5 = almost always
3 To what extent do you produce sputum when coughing?	0 = no sputum 1 = a moderate amount of sputum 2 = a larger amount of sputum 3 = a very large amount of sputum

Cough assessment will be conducted at Admission prior to product test and 24 hours ( $\pm 1$  hour) after product use ( $T_0$  fix) for each variant (Day 2 through Day 5). Cough assessment should be done in the morning prior to any product use.

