##### **Confidentiality Statement**

The number and percent of values BLOQ or above ULOQ will be presented in each summary table.

For CYP2A6 activity, any values BLOQ or above the ULOQ in the denominator will not be imputed and the derived variable will be presented as "Not Calculated" in descriptive summaries.

Questionnaire data total scores and domain or subscale scores may use a certain degree of imputation (by averaging across individual item scores) as detailed in Section 7.3 "Questionnaires". For assessment of cough, if no cough was reported at a given visit then the VAS score is imputed with zero.

If an actual sampling time or  $T_0$  fix or  $T_0$  ad lib is missing from the dataset, the corresponding nominal sampling time will be used instead.

If time of discharge is missing, then it will be imputed by 8pm of the day the subject was discharged.

Partial dates will not be imputed, but assumptions will be made as follows to assign to either medical history or concomitant diseases (Table 17), to assign to either product-emergent or non-product emergent adverse events (Table 18) and to assign to either prior or concomitant medications (Table 19):

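### The cough Likert changes from baseline exist only for subjects who cough both at Admission and after the variant, because the SAP's zero rule for 'no cough' covers the VAS alone

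*SAP*

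**What the plan says.** SAP 5.2 lists among the safety endpoints "Cough changes from baseline (VAS and three Likert scales").

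The items are conditional on an opening question about regular cough in the preceding 24 hours. SAP 7.3.5 states: "If the answer is 'yes', they will be asked to complete a visual analogue scale (VAS), three Likert scale questions and an open question". Protocol 7.8.5 has the same structure: after a yes, "they will be asked to complete a cough assessment questionnaire".

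SAP 12.1.5 deals with a no for one item only: "For assessment of cough, if no cough was reported at a given visit then the VAS score is imputed with zero". It gives no value for intensity, frequency or sputum. The general position in Protocol 12.1.4 is "In general, missing data will not be imputed in this study". Its exception concerns total, domain and subscale scores obtained by averaging, which these single items are not.

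SAP Table 10 defines intensity as "1 = very mild 2 = mild 3 = moderate 4 = severe 5 = very severe". Frequency also runs from 1 to 5, starting at rarely. Neither has a level for no cough. Sputum runs from 0 to 3 and does have a zero, but it is asked only after a yes.

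SAP 12.6.5.5.6 plans the number and percentage of subjects with cough at baseline and after use. It then plans summaries of the VAS and Likert responses at baseline and as change from baseline by variant, "for all subjects who filled in the questionnaire".

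**The concern.** A change score needs two values from the same subject (SAP section 7). For cough the baseline value is the Admission assessment, the only one before first use on Day 1 (SAP 4.1 and 7.3.5). If the Likert items have no value when cough is denied, a subject who starts coughing after inhaling the powder has no Likert change, and nor does a subject whose cough stops. Whether a subject enters the summary then depends on the outcome being summarized.

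Tolerability of an inhaled powder is a study objective, and the variants differ in particle size, nicotine content and flavor. Cough that begins after use is the reaction of most interest, and it is missing from three of the four cough change endpoints. The adverse event tables are only a partial backstop, because Protocol 7.8 does not require symptoms recorded on questionnaires to be reported as adverse events. Its reason is that the questionnaires will themselves be analyzed.

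**Working it through.** The plan states no figure to reproduce here. The check has three steps.

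**1. Each cough pattern traced through the SAP rules** (VAS zero rule applied; no Likert rule, so no imputation)

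| Admission | After variant | VAS change | Likert change |
|---|---|---|---|
| cough | cough | computable | computable |
| no cough | cough (new onset) | computable, from 0 | not computable |
| cough | no cough (resolved) | computable, to 0 | not computable |
| no cough | no cough | 0 | not computable |

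Only the first row feeds the Likert change.

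**2. Expected counts per variant**

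Inputs:
- N = 18, the randomized number (SAP section 8).
- Baseline cough rate p = 10–40%, new onset among non-coughers r = 10–30%, persistence among baseline coughers s = 50–90%. All three are assumptions, because the documents give no cough rates.

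Results:
- Evaluable Likert changes = N × p × s. Lowest: 18 × 0.10 × 0.50 = 0.9. Highest: 18 × 0.40 × 0.90 = 6.48, about 6.5.
- New-onset cases without a Likert change = N × (1 − p) × r. Lowest: 18 × 0.60 × 0.10 = 1.08, about 1.1. Highest: 18 × 0.90 × 0.30 = 4.86, about 4.9.
- Share of post-use coughers with no Likert change = new onset / (new onset + persisting). Lowest: 1.08 / (1.08 + 6.48) = 14%. Highest: 4.86 / (4.86 + 0.9) = 84%.
- Chance of fewer than 4 evaluable changes, from a binomial with 18 trials and probability p × s: 0.07 when p × s = 0.36, and 0.99 when p × s = 0.05. Below 4 values, SAP 12.1.5.1 keeps counts, percentages, median, quartiles and range, but not the mean and SD.

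**3. Can the direction mislead?** An invented example with N = 18:
- 3 subjects cough at Admission (intensity 3, VAS 40).
- After use, 2 of them still cough (intensity 2, VAS 30) and 1 has stopped.
- 5 start coughing (intensity 3, VAS 40) and 10 never cough.

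| Summary | Result |
|---|---|
| Subjects with cough | 3/18 (16.7%) rising to 7/18 (38.9%) |
| VAS change, zero rule applied | (−10 − 10 − 40 + 5 × 40) / 18 = +7.8, n = 18 |
| Likert intensity change as planned | −1 in both evaluable subjects, n = 2 |
| Likert intensity change, no cough coded 0 | (−1 − 1 − 3 + 5 × 3) / 18 = +0.56, n = 18 |

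The planned Likert summary shows improvement while incidence and the VAS both worsen.

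**The case against.** The loss is narrow. A new-onset cougher is still counted among subjects with cough, appears in Listing 15.3.6.11 with the recorded Likert answers, and contributes to the VAS change if the zero rule is applied. Adverse events are the primary safety assessment, and no hypothesis is tested. All of this stands, and it limits the point to the Likert change summaries.

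A reader might infer that new-onset cough vanishes from the cough analysis. The documents do not support that, for the reasons just given. SAP 12.1.3 also has a general default of summarizing each post-baseline timepoint. If it applies here, post-use Likert values of new-onset coughers would be tabulated too. SAP 12.6.5.5.6 names only baseline and change, so this is unclear.

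A reader might also take the SAP to state that the Likert items are left missing. It does not. That follows from its silence together with the protocol default, and the separate table shells, not available here, might contain a coding rule.

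Finally, scoring 0 on 1-to-5 ordinal scales can be criticized. It assigns a value the subject never gave, the step from 0 to 1 is arbitrary, and a no to regular cough does not rule out an occasional one. This is a fair objection to a numeric code as the main remedy. It has less force against a separate 'no cough' category.

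**Conclusion.** The point holds for the three Likert change-from-baseline endpoints. Read with the protocol default, the SAP bases them on subjects who cough at both times, while its zero rule keeps everyone who answered the opening question in the VAS change. The endpoints listed together in SAP 5.2 therefore describe different subjects, and the Likert subset is selected by outcome.

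Under the assumed rates, about 0.9 to 6.5 subjects per variant would have a Likert change and about 1.1 to 4.9 new-onset cases would be lost. These are expected counts, not limits. It would be tempting to say that every subject without baseline cough is a lost case, but that would require all of them to develop cough. The safety population may also exceed 18 for P3P 3, since subjects are exposed before randomization.

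There is a second inconsistency. The restriction in SAP 12.6.5.5.6 covers the VAS and Likert items together. Read literally, it also excludes the zero-imputed VAS subjects and so conflicts with the rule in 12.1.5 that "if no cough was reported at a given visit then the VAS score is imputed with zero". The wording needs attention on either reading.

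This is a cheap improvement to a descriptive safety table. It does not affect the primary PK analysis.

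**What to change.** In SAP 12.1.5 and 12.6.5.5.6:
- Treat a no to the opening cough question as a 'no cough' level, placed below the lowest category for intensity and frequency and added as a level for sputum.
- Report baseline-to-post shift tables by variant for the three Likert items. A change score with no cough coded 0 can be an optional supplement.
- Replace the restriction to subjects who completed the questionnaire with one denominator for all four items: safety-population subjects who answered the opening question at the visits concerned.

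No new data are needed. The cost is a sentence in each section and some work on Table 15.2.6.19. There are two small downsides. The added level lies outside the printed 1-to-5 scales, and a no to regular cough does not strictly exclude occasional cough. The second already applies to the VAS zero rule. A footnote to the table can state both.

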## **13 ANALYSIS AND REPORTING**

### **13.1 Interim Analysis and Data Monitoring**

The interim PK analysis is being conducted with the main aim of evaluating whether the plasma nicotine concentration data are amenable to background-concentration correction via the Non-Compartmental Analysis (NCA) method, as described in the P3P-PK-01-CH study protocol and which is dependent on the estimation of the terminal elimination rate constant  $\lambda_z$  (see Section 13.1.3.1 "Primary PK Analysis Methodology (NCA-based method)" for further details). If plasma concentrations cannot be background-corrected in a sufficient number of subjects e.g., in the event that  $\lambda_z$  (or  $t_{1/2z}$ ) cannot be estimated, alternative approaches will be evaluated including conventional Compartmental Analyses (CA) or population PK methods. These alternative PK analysis methods are also described in more detail in the following sub-sections.

A Clinical Research Associate ("Monitor") from [REDACTED] will be responsible for the monitoring of the study. Monitoring will be performed according to [REDACTED] standard operating procedures (SOPs) and as per the agreed monitoring plan with PMI.

The PI, or a designated member of the PI's staff, must be available during the monitoring visit to review the data and resolve any queries, and to allow direct access to the subject's records for source data verification.

All changes to the source data will have to be approved by the PI.

#### **13.1.1 Interim Analysis Objectives**

The objective of this interim PK analysis is to select the methods that will enable the background-correction of nicotine concentrations for the purposes of accurately estimating PK parameters for each specific P3P variant and regimen by adjusting for possible carry-over effects due to limited wash-out periods between product use of different product use regimen or P3P variants.

#### **Confidentiality Statement**

Data and information contained in this document are considered to constitute trade secrets and confidential commercial information, and the legal protections provided to such trade secrets and confidential information are hereby claimed under the provisions of applicable law. No part of this document may be publicly disclosed without the written consent of Philip Morris Products S.A.

Three different PK analysis methodologies will be evaluated sequentially, from simplest to most complex. More complex approaches will only be evaluated if the preceding simpler approach is deemed to be unsuccessful.

The evaluation will be performed sequentially in the following order:

- To evaluate whether the per protocol NCA plasma nicotine background-correction method can be used (this analysis methodology is described in Section 13.1.3.1 "Primary PK Analysis Methodology (NCA-based method)";
- To evaluate whether CA can be used to estimate the terminal elimination half-life of plasma nicotine to enable background-correction and subsequent estimation of PK parameters by NCA (see Section 13.1.3.2 "Alternative PK Analysis Methodology (CA-based method)");
- To evaluate if available plasma nicotine data is a priori amenable to background-correction via population PK methods (nonlinear mixed-effect modeling), see Section 13.1.3.3 "Population PK Analysis Methodology (Non-Linear Mixed Effects Modelling)".

### **13.1.2 Interim Analysis Materials**

#### **13.1.2.1 Bioanalytical Data**

The interim analysis is to be performed on the quality controlled data, as provided by the bioanalytical laboratory, prior to database lock.

#### **13.1.2.2 Analysis Dataset**

The specifications of the PK analysis dataset will be described in a Data Transfer Agreement (DTA) that will be completed prior to the start of any interim PK analysis activities.

### **13.1.3 Interim Analysis Methods**

The methods for PK parameters derivation are described in Section 7.1.2 "PK Parameters".

#### **13.1.3.1 Primary PK Analysis Methodology (NCA-based method)**

The nicotine terminal elimination rate constant  $\lambda_z$  (and  $t_{1/2z}$ ) will be estimated as described in Section 7.1.2.3 "Criteria for Calculating the Apparent Terminal Elimination Half-Life". For the purposes of background-correction of the plasma concentrations post-baseline the following formula will be applied:  $cC_t = C_t - C_0 \cdot e^{-\lambda_z \cdot t}$ . Where  $cC_t$  is the corrected concentration at each time point,  $C_t$  is the concentration at each time point,  $C_0$  is the pre-use baseline concentration,  $\lambda_z$  is the terminal elimination rate constant and  $t$  is the actual time.

If the predicted  $cC_t$  is  $< 0.2$  ng/mL (the bioanalytical LOQ threshold), this value will be used for the estimation of the background-corrected PK parameter (NCA analysis) only if the corresponding  $C_t$  is above LOQ, and the predicted  $cC_t$  will be imputed by zero if

